Statistical analysis plan

Increase Level of Physical Activity and Decrease Use of Health Care for People With COPD

ClinicalTrials.gov identifier	NCT03746873
SAP version/date	V 1.0, 21-12-XX
Principal investigator,	[name] PhD, Department of Community and Rehabilitation, Umeå university, Sweden

Revision of Statistical analysis plan

[Revisions in SAP v1.0](#)

Revisions compared to previously described statistical analysis plan, published in the study protocol in BMJ Open.(1)

Due to the COVID-19 pandemic, the recruitment and retention of participants to the COPD Web RCT have not proceeded as planned. Recruitment through healthcare centres was almost stopped due to the pandemic, why an ethical amendment was search for and approved (Dnr 2019-05572).

The amendment made recruitment possible through advertisement in newspapers and the Internet. Another issue is the high dropout rates and many participants has raised the effects of the pandemic as a reason for not continuing in the study. We included the aimed number of participants (144) but instead of the expected 20% dropout, we ended up with approximately 30% dropout at 3 months.

- The primary statistical analysis has been changed from a mixed effects models to an ANCOVA analysis at 3 months follow-up, adjusting. In this analysis we will use age and sex as covariates for the physical activity level.(2): The motivation to change to 3-months as primary analysis is the larger than expected dropout rate. The adjustments of age and sex is intended to increase power and precision in treatment effect estimates, as they are considered predictive covariates for outcome.
- For evaluation of the effect at 12 months follow-up we will use mixed model repeated measures, incorporating the measurements at baseline and 3-months follow-up. However, the model will not include random effects of subjects and primary health care units. Instead, repeated measurements will be modelled using an unstructured covariance matrix for the error terms. The updated model is motivated partly by that data on primary health care units is not available and partly that the new model will be more robust against misspecification, if model assumptions is found not fulfilled.

Content

Revision of Statistical analysis plan	2
Revisions in SAP v1.0	2
Content.....	Fel! Bokmärket är inte definierat.
Introduction.....	3
Objectives.....	3
Sample size calculation.....	4
Randomisation and masking	4
Data management and monitoring.....	4
Statistics and analysis.....	4

Introduction

The use of adequate self-management strategies for people with chronic obstructive pulmonary disease (COPD) may increase the level of physical activity, improve health related quality of life and reduce health-care use. Whether web-based support, in addition to prompts (e-mail and SMS), could be used to promote self-management strategies to facilitate behaviour change in people with COPD is not clear.

Objectives

This clinical trial aims to generate evidence on the effect of a web-based solution, the COPD-web, in a cohort of people with COPD in primary healthcare context.

Outcomes

Primary outcome:

Physical activity (PA) level measured objectively (steps/day measured with DynaPort, McRoberts) and subjectively (questionnaire from the Swedish National Board of Health and Welfare).

Secondary outcomes:

Health-related quality of life measured with self-administered Chronic Respiratory Questionnaire (CRQ-SA)

COPD-related symptoms measured with COPD Assessment Test (CAT)

Dyspnea measured with modified Medical Research Council Dyspnea scale (mMRC)

Self-reported health-care contacts related to COPD.

Sample size calculation

The sample size was calculated with the premises that a total of 144 participants with COPD would be required to detect a mean difference of 1131 steps with a standard deviation of 2193 steps(3), $\alpha = 0.05$, $\beta = 0.20$ (80% power), and a two-tailed test of significance including an estimated dropout rate of 20%.(4)

Randomisation and masking

A permuted block design with a random block size varying from 4 to 8 in a 1:1 allocation ratio will be computer generated to randomise participants. This approach is chosen to achieve balanced and evenly distributed samples. A third party, not involved in data collection or analysis of the results, will perform the randomisation and the result will be stored in sealed envelopes. Due to the character of the intervention, blinding of trial participants will not be applicable. Furthermore, as all data are self-reported, neither is blinding of outcome assessors applicable.

Data management and monitoring

To ensure confidentiality, participants with COPD will get a unique identification (ID) when included in the study. The code list linking participants and ID number will be kept separate from the data.

Data will be analysed by ID only. All records that contain names or other personal identifiers, such as locator forms and informed consent forms, will be stored separately from study records identified by the ID number. The local database will be secured with a password-protected access system. All data will be coded and reported on group level. Thus it will not be possible to identify specific participants in the trial. We will use two-pass verification to ensure correct data entry. No interim analyses or stopping guidelines are pre-specified. Only the researchers will have access to the final trial dataset.

Statistics and analysis

Analysis population

The primary analysis will be an intention-to-treat analysis (including all participants randomised). In addition, a complete case population (participants with full outcome measurements independent on adherence to intervention), and a per-protocol analysis (defined as at least one login besides creating an account on the COPD Web or answering that the SMS and email with referral links have been used at least rarely (1-3 times) at the follow-ups) will be performed. No sub-group or adjusted analyses other than the pre-specified complete case and per-protocol analysis will be performed.

Missing data

Missing data will be imputed in the intention-to-treat analysis using multiple imputation assuming data is missing at random conditional on participants' severity of disease and self-reported history of

exacerbations. This is because the severity of disease and history of exacerbations are known risk factors for future exacerbations and may affect adherence to PA interventions.(5)

[Analysis methods at 3 month follow up](#)

The difference in the primary outcome between the intervention and control group will be estimated using an ANCOVA analysis with 3 months follow up as dependent variable, and group (experimental group vs control group) and baseline measurement as independent variables. In this analysis we will use age and sex as covariates.

[Analysis methods at 12 month follow up](#)

For the analyses of 12 months follow-up, we will use Mixed model repeated measures with an unstructured co-variance matrix for error terms. Fixed effects will be time point (baseline, 3-months or 12 months), group (experimental group vs control group) and a Timepoint*group interaction. To judge the model assumptions of normality, we will analyse model residuals using qq-plots and histograms.

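### On the SAP's own inputs, a sample size that includes 20% dropout is 148 to 150, not 144 (minor; wording only)

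*SAP*

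**What the plan says.** The section Sample size calculation reports, in the past tense, that "a total of 144 participants with COPD would be required to detect a mean difference of 1131 steps". The inputs are a "mean difference of 1131 steps with a standard deviation of 2193 steps", alpha 0.05 and 80% power, "and a two-tailed test of significance including an estimated dropout rate of 20" per cent. Randomisation is 1:1 (Randomisation and masking). The section shows neither the number of evaluable participants nor the step from that number to 144. It also does not say whether 2193 is the standard deviation of step levels or of change in steps.

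The section Revisions in SAP v1.0 reports that the target of 144 was reached, but that "instead of the expected 20% dropout, we ended up with approximately 30% dropout at 3 months". It gives this as the reason for the new primary time point: "The motivation to change to 3-months as primary analysis is the larger than expected dropout rate". The primary analysis is now an "ANCOVA analysis with 3 months follow up as dependent variable", with baseline, age and sex in the model. On power it says only that "The adjustments of age and sex is intended to increase power and precision in treatment effect estimates".

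**The concern.** A sample size that includes a given dropout rate should leave the required number of evaluable participants once that fraction is lost. The evaluable number must therefore be divided by one minus the dropout rate. Multiplying it by one plus the rate gives too few. The stated 144 looks like the second calculation, so the sentence claims slightly more protection against dropout, and slightly more power, than its inputs give.

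Only the correctness of a stated sample size and power figure is at stake. Enrolment is closed, and neither the treatment estimate nor the test depends on the figure. Still, the sentence is likely to be carried into the trial report, where a reader who redoes the sum will not get 144.

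**Working it through.** **Inputs** (SAP, Sample size calculation, and Randomisation and masking): difference 1131 steps, SD 2193 steps, two-sided alpha 0.05, power 80%, dropout 20%, allocation 1:1. Standardised difference: 1131/2193 = 0.5157.

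**Step 1. Evaluable number.**
- Normal approximation: n per arm = 2 x [2193 x (1.960 + 0.842)/1131]² = 59.02, so 118.04 in total before rounding. Rounded up per arm, this is 60 and 120.
- Two-sample t-test: 59.99 per arm, so 60 and 120 in total.

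**Step 2. Reproduce the stated figure.** 120 x 1.2 = 144, an exact match. The SAP does not print this step, so it is an inference from the match.

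**Step 3. Size that includes 20% dropout.**
- t-test: 120/(1 − 0.20) = 150.
- Unrounded normal approximation: 118.04/0.80 = 147.5, so 148.
- Shortfall of 144: 4 to 6 participants.

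**Step 4. Dropout that 144 can absorb.**
- t-test: 1 − 120/144 = 16.7%.
- Unrounded normal approximation: 1 − 118.04/144 = 18.0%.

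**Step 5. Power of 144 at 20% dropout.** 144 x 0.80 = 115.2, or 57.6 per arm. Standard error = 2193 x √(2/57.6) = 408.6 steps, and 1131/408.6 = 2.768.
- Normal: Φ(2.768 − 1.960) = 79.0%.
- t-test (noncentral t): 78.35%, rounded to 78.4%.
- Gap to the stated 80%: 1.0 to 1.7 points.

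**Step 6. The same calculation at the reported dropout of about 30%** (for the optional note only). 144 x 0.70 = 100.8, or 50.4 per arm. Standard error = 2193 x √(2/50.4) = 436.9 steps, and 1131/436.9 = 2.589.
- Power: 73.5% (normal), 72.7% (t-test).
- Difference detectable with 80% power (t-test): about 1236 steps.

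**Step 7. What the 3-month ANCOVA would need.** Take 50.4 per arm, with three degrees of freedom used for baseline, age and sex. Power for 1131 steps is 80% when the residual SD is about 2006 steps, and higher when it is smaller. This threshold holds whichever type of SD 2193 is. Whether the residual SD will fall below it cannot be read from the SAP. For illustration, with assumed correlations between baseline and 3 months and no further gain from age and sex:

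| 2193 taken as | Residual variance | Assumed r | ANCOVA power |
|---|---|---|---|
| SD of levels | 2193² x (1 − r²) | 0.3 / 0.5 / 0.7 | 76.6% / 84.1% / 94.8% |
| SD of change (equal variances at both times) | 2193² x (1 + r)/2 | 0.5 / 0.7 / 0.9 | 84.1% / 79.4% / 74.8% |

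The direction in r reverses with the type of SD. Steps 6 and 7 count about 101 observed outcomes and ignore any gain from the planned multiple imputation.

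**The case against.** The strongest reply is that the slip changes nothing. It amounts to 4 to 6 participants and less than 2 points of power, the normal-approximation answer of 148 is within 3% of 144, and enrolment is complete. All of that stands, and it is why the point is minor. It does not make the sentence right: on these inputs, neither standard calculation leaves enough evaluable participants after a 20% loss from 144, and restating it costs almost nothing.

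A reader might go further and infer that the SAP is at fault for not restating power after dropout rose to about 30% and the primary analysis moved to 3 months. The document does not support calling that an error. The sample size section describes a past design calculation, the revision section reports the higher dropout openly, and nothing in the SAP claims 80% power for the ANCOVA. With recruitment finished, the confidence interval will show the precision obtained. A restated figure would be useful to readers, but it is an option.

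A reader might also take the figure of about 73% at 30% dropout as the power of the planned analysis. It is not. It repeats the design calculation with fewer participants, whereas the ANCOVA also adjusts for baseline, age and sex. The illustrative values in the working lie on both sides of 80%, and the SAP gives neither the correlation nor the type of SD needed to choose among them.

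**Conclusion.** The point holds as a minor arithmetic error in a stated figure. With the SAP's own difference, SD, alpha, power and allocation, the size that includes 20% dropout is 150 by the t-test, or 148 by the unrounded normal approximation. The stated 144 corresponds to about 17% to 18% dropout, or to about 78% to 79% power at 20% dropout. This rests on two equal arms with equal loss and a two-sample comparison of means. The explanation that 120 was multiplied by 1.2 is likely but not documented; the conclusion does not depend on it.

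No shortfall of the 3-month ANCOVA is established. Its power for 1131 steps could be below or above 80%, depending on whether its residual SD exceeds about 2006 steps.

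**What to change.** In Sample size calculation, mark the paragraph as the design-stage calculation and restate the result, for example:

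> *By a two-sample t-test, 120 evaluable participants are needed. Enrolling 144 allows for about 17% dropout; at 20% dropout, power is about 78%.*

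Optionally, add:

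> *At the reported dropout of about 30% at 3 months (about 101 participants with outcome data), the same design calculation gives about 73% power, or 80% power for a difference of about 1236 steps. The 3-month ANCOVA has 80% power for 1131 steps if its residual SD is at most about 2006 steps.*

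If this is added, also state whether 2193 is the SD of levels or of change. A cross-reference is enough if the published protocol says so.

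The cost is one reworded sentence, plus two or three if the optional note is taken up. The stated design figure becomes slightly less favourable. Enrolment, the analysis and the analysis sets do not change.

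### If the 12-month MMRM is fitted to imputed data, as the Missing data section literally allows, earlier activity can inform missing 12-month values only through an imputation model that does not name it

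*SAP*

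**What the plan says.** Under Statistics and analysis, the Analysis population section makes the primary analysis intention-to-treat, covering everyone randomised. The Missing data section, placed before both analysis-method sections, says "Missing data will be imputed in the intention-to-treat analysis using multiple imputation". It assumes data are missing at random given disease severity and self-reported exacerbation history. It names no other imputation variable and no visit.

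For month 12 the plan states: "we will use Mixed model repeated measures with an unstructured co-variance matrix for error terms". The fixed effects are time point (with baseline as one of three levels), group, and their interaction. Revisions in SAP v1.0 gives the intention: "we will use mixed model repeated measures, incorporating the measurements at baseline and 3-months follow-up". That section also moves the primary analysis to a 3-month ANCOVA and reports that about 30% had dropped out by then. No 12-month dropout figure is given.

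The SAP does not say whether the 12-month model is fitted to observed or to imputed values.

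**The concern.** An MMRM with unstructured covariance handles dropout by likelihood. A participant's observed baseline and 3-month values, through their correlation with month 12, help estimate the 12-month arm mean. This happens only while the data are incomplete. Once every 12-month value has been filled in, the model has nothing left to borrow, and whatever is known about dropouts must already be in the imputed values.

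The content of the imputation model therefore decides the result. If it holds only the two named variables, the declared purpose of using the earlier measurements is lost for the participants who need it most. What is at stake is precision, bias when dropout is related to earlier activity, and dilution of the effect if treatment group is not in the imputation. The 12-month comparison is no longer primary, but it is the only long-term comparison the SAP specifies.

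**Working it through.** **The plan's own figure.** Sample size calculation aims to "detect a mean difference of 1131 steps with a standard deviation of 2193 steps" with two-sided alpha 0.05 and 80% power. Per arm: 2 × (1.960 + 0.842)² × (2193/1131)² = 59.02, so 60. Total 120, and 120 × 1.20 = 144, as stated. The figure does not bear on this point; it supplies the arm size (72), the SD and the reference effect used below.

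**Assumed inputs, not in the documents.** Correlations between visits, missingness at month 12 (30% to 40%), the dropout mechanism, and how strongly severity predicts activity.

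**Step 1: the model on completed data.** Each participant contributes three values, and each visit has the same regressors (intercept and group). With identical regressors for every visit, generalised least squares equals ordinary least squares visit by visit, whatever the covariance matrix. The 12-month contrast is then the raw difference in 12-month means. A numerical check gave 1216.96 by generalised least squares and 1216.96 by raw means. The time-by-group contrast is the difference in mean change, which uses baseline by subtraction only.

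**Step 2: precision.** Take one earlier measurement with correlation r to month 12, a fraction m missing at random, and n per arm.

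- Likelihood on observed data: variance of an arm mean = SD² × [(1 − r²)/(n(1 − m)) + r²/n].
- Imputation that ignores the earlier value: SD²/(n(1 − m)).
- Variance ratio = 1/(1 − r²m).

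Results:

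- r = 0.5, m = 0.3: 1/(1 − 0.075) = 1.08, SE +4%.
- r = 0.7, m = 0.4: 1/(1 − 0.196) = 1.24, SE +11.5%.
- r = 0.8, m = 0.4: 1/(1 − 0.256) = 1.34, SE +16%.

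This treats severity as having no predictive value, so it is the upper side for each r.

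**Step 3: dilution if group is not in the imputation.** Imputed values then carry almost no group difference, so the effect shrinks to about (1 − m) × 1131 under random dropout: 0.7 × 1131 = 792, or 0.6 × 1131 = 679.

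**Step 4: simulation.** 72 per arm, SD 2193, true effect 1131, 30% missing at month 3, 20 imputations, 500 trials per setting. Correlations (baseline–3 months, baseline–12 months, 3–12 months) are A = 0.6/0.5/0.6 and B = 0.75/0.7/0.75. In the dependent settings, participants in the intervention arm with low 3-month activity are more likely to leave later (log-odds 1.5 per SD). Entries are the mean 12-month difference (empirical SD); the Monte Carlo error of a mean is about 450/√500 ≈ 20.

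| Correlations, missing at month 12, later dropout | MMRM, observed data | Imputation: two named variables | Those plus group | Those plus group, baseline, 3-month |
|---|---|---|---|---|
| A, 30%, none | 1136 (425) | 791 (322) | 1138 (444) | 1132 (428) |
| A, 40%, random | 1159 (454) | 693 (299) | 1161 (462) | 1156 (460) |
| A, 40%, dependent | 1131 (463) | 791 (305) | 1349 (478) | 1123 (467) |
| B, 30%, none | 1101 (420) | 759 (333) | 1092 (451) | 1099 (420) |
| B, 40%, random | 1131 (426) | 659 (308) | 1112 (471) | 1132 (428) |
| B, 40%, dependent | 1103 (429) | 814 (293) | 1391 (459) | 1098 (432) |

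- Two named variables only: 659 to 814, which is 42% to 28% below 1131. The sampling SD falls too, so here the problem is bias rather than precision.
- With group added: SD 2% (462/454) to 11% (471/426) above the observed-data MMRM, and 2% to 14% for change from baseline. Under dependent dropout the error is +218 (19%) or +260 (23%).
- With group and earlier activity added: SD within about 1.5% of the observed-data MMRM, and no material bias.

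A second simulation (400 trials, correlations 0.7/0.6/0.7, 40% missing at month 12, group in the imputation) gave SE 470 against 436, or +8%. With dropout depending on baseline in the intervention arm only (log-odds −0.7 per SD), the mean error was +249 against +18: a gap of 231 steps, or 231/1131 = 20%.

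**The case against.** The strongest reply is that the SAP never says the MMRM runs on imputed data. The intention-to-treat label is attached to the primary analysis, which is now at month 3, and the 12-month section does not mention imputation. Imputation for the ANCOVA and likelihood for the MMRM is a coherent reading. This stands as far as it goes: a reader might infer that the plan definitely imputes first, and the text does not establish that. But on the milder reading the 12-month analysis has no stated population or missing-data rule, so the same clarifying sentence is needed.

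The two named variables are given as the missing-at-random condition, not as a complete imputation model. That also stands. The harm arises if the analyst treats them as complete, which the wording permits.

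A reader might also infer that imputing before an MMRM is itself the fault and can bring no benefit. That is wrong on both counts. With group and earlier activity in the imputation, the result matches the observed-data MMRM. Imputation can also bring in severity and exacerbation history, which the listed MMRM omits. In 250 simulated trials per setting (72 per arm, zero true effect, about 40% missing at month 12, dropout depending on severity in one arm), the listed MMRM on observed data was biased by −104 to −263 steps. A joint model with severity by time was biased by −2 to −23 (Monte Carlo SE 21 to 26). Adding severity as a constant effect gave −21 when its influence was the same at every visit, but −118 and −152 when it was stronger at month 12.

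Finally, the precision loss is modest, and every magnitude rests on assumptions. Both are true.

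**Conclusion.** The concern holds in limited form. The SAP leaves open which data the 12-month MMRM uses. On its literal reading, earlier activity and treatment group are absent from the only step that could use them for missing 12-month values. The weakness is the named conditioning set, not the order of imputation and modelling.

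The precision loss is the smaller issue. Arm-specific dropout related to earlier activity, or leaving group out of the imputation, could move the estimate by a fifth or more, upward in the first case as simulated and toward zero in the second. The identity in Step 1 needs no assumption; the sizes depend on the correlations, 12-month missingness and dropout patterns assumed above. The documents do not show that such dropout occurred. The 3-month primary analysis is outside this point. The clarification should be made, because it is cheap and removes an analyst choice that could materially change the 12-month result.

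**What to change.** State one of the following for month 12:

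- **(a) No prior imputation.** The MMRM is fitted by restricted maximum likelihood to all observed baseline, 3-month and 12-month values of all randomised participants. If the stated missing-at-random condition is to be kept, severity and exacerbation history enter with their interactions with time; constant effects do not preserve it in general.
- **(b) With imputation.** The imputation model includes group, baseline activity and 3-month activity together with severity and exacerbation history.

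The sentence in Analysis population that rules out further adjusted analyses should be aligned with the choice. The cost is one or two sentences of SAP text, a few extra model terms, and no new data.

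### The 12-month repeated-measures model fits a separate baseline mean per arm, omits age and sex, and does not name the contrast to be reported; either possible contrast is less precise than a baseline-adjusted one

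*SAP*

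**What the plan says.** Under *Analysis methods at 12 month follow up*, the SAP specifies the covariance, "we will use Mixed model repeated measures with an unstructured co-variance matrix for error terms", and then the mean model: "Fixed effects will be time point (baseline, 3-months or 12 months), group (experimental group vs control group) and a Timepoint*group interaction". *Revisions in SAP v1.0* confirms that baseline enters as a response: "we will use mixed model repeated measures, incorporating the measurements at baseline and 3-months follow-up". Neither place constrains the baseline means to be equal, uses baseline as a covariate, lists age or sex, or names the coefficient or contrast that will be reported as the 12-month effect.

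The 3-month analysis is built differently. Its ANCOVA has "group (experimental group vs control group) and baseline measurement as independent variables", and the section adds: "In this analysis we will use age and sex as covariates". The revision note gives the reason: "The adjustments of age and sex is intended to increase power and precision in treatment effect estimates". *Analysis population* states: "No sub-group or adjusted analyses other than the pre-specified complete case and per-protocol analysis will be performed".

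**The concern.** Time point, group and their interaction over three visits give six free means, so each arm has its own baseline mean. Under 1:1 randomisation any baseline difference between the arms is chance. A model that leaves it free does not use the baseline value efficiently to sharpen the treatment comparison.

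The fitted model offers two candidates for the 12-month effect: the interaction at 12 months (difference in change from baseline) and the simple group difference at 12 months. They give different numbers whenever the arms differ at baseline. With neither named, the choice could be made after both are seen.

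The plan also treats the same outcome in two ways. At 3 months it adjusts for baseline, age and sex, the last two expressly for precision. At 12 months, where dropout can only be as high or higher, it does none of this. The reasons given for revising the 12-month model (no data on primary health care units, robustness to misspecification) bear on the random effects and covariance, not on the covariates.

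**Working it through.** **Inputs from the SAP.** Difference 1131 steps and SD 2193 steps, two-sided alpha 0.05, 80% power, N = 144 allocated 1:1 (72 per arm), about 30% dropout at 3 months (72 × 0.70 = 50.4 per arm remain).

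**Inputs assumed.** SD 2193 at every visit; the same correlation ρ between any two visits; 40% dropout at 12 months (72 × 0.60 = 43.2 per arm, about 86 in all); complete baseline; monotone dropout completely at random. The SAP gives neither ρ nor the 12-month dropout, so ranges are shown.

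**The plan's own figure.** The normal approximation gives 2 × (1.96 + 0.84)² × (2193/1131)² ≈ 59 per arm; the t-based calculation gives 60. Then 2 × 60 = 120 and 120 × 1.20 = 144, the stated total. So 1131 and 2193 were used as the difference and SD of a two-sample comparison, and they are used the same way here.

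**Complete data, closed form.** In units of 2σ²/n the variances are:

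- group difference at 12 months: 1
- difference in change from baseline: 2(1 − ρ)
- baseline-adjusted difference: 1 − ρ²

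The adjusted variance is below the first by ρ² and below the second by 2(1 − ρ) − (1 − ρ²) = (1 − ρ)². It is therefore the smallest for every ρ between 0 and 1.

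**With dropout.** The generalised least squares information matrix was summed over the three dropout patterns (baseline only; baseline and 3 months; all three visits), once with free baseline means and once with a common baseline mean. Power is Φ(1131/SE − 1.96).

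| ρ | SE, change | SE, 12-month difference | SE, common baseline | Power (same order) |
|---|---|---|---|---|
| 0.5 | 445 | 445 | 405 | 72 / 72 / 80% |
| 0.6 | 401 | 433 | 374 | 80 / 74 / 86% |
| 0.7 | 350 | 420 | 333 | 90 / 77 / 92% |
| 0.8 | 289 | 404 | 279 | 98 / 80 / 98% |

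At ρ = 0.9 the SEs are 206, 386 and 202. From ρ 0.5 to 0.8, the variance of the common-baseline contrast is 0.83, 0.87, 0.90 and 0.94 of that of the change contrast, and 0.83, 0.74, 0.63 and 0.48 of that of the 12-month difference.

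**Sensitivity.**

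- The ordering is the same with no dropout, with 30% at both visits, and with 30% then 50%.
- If the baseline–12-month correlation is 0.1 lower and the 3–12-month correlation 0.05 lower, the SEs at ρ = 0.7 are 401, 433 and 373.
- If 2193 is the SD of a change rather than of a level (the SAP does not say), the ratios are unchanged. Power over ρ 0.5 to 0.8 becomes 70–72% (change), about 42–72% (12-month difference) and 73–80% (common baseline).

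**Gap between the two open contrasts.** With complete baseline data, the 12-month difference minus the difference in change is exactly the observed baseline difference. Its SE is 2193 × √(2/72) = 365.5 steps. Its expected absolute size is 365.5 × √(2/π) ≈ 292 steps, and 292/1131 = 26%.

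**Age and sex.** If they explain 5–15% of the variance at every visit (assumed), adding them by time lowers the common-baseline SE by at most 3%: at the 15% end, from 405 to 394 at ρ = 0.5 and from 333 to 328 at ρ = 0.7.

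**The case against.** The strongest reply is that this is a valid and common model, and that its usual effect is the interaction. On that reading the SE penalty falls from about 10% at ρ = 0.5 to 3% at ρ = 0.8, and at high correlation power barely moves. The large loss belongs to a reading the SAP never adopts. This is right about size, but the SAP does not adopt the interaction either. Its own 3-month effect is an adjusted group difference, not a change score, so the interaction cannot be taken as understood.

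A second reply is that randomisation justifies equal baseline means only in the full randomised set, whereas the SAP also plans complete-case and per-protocol analyses, and per-protocol membership depends on use of the intervention. This does not count against the remedy. With baseline observed, the equal-baseline likelihood separates into a baseline part and a regression of the later visits on baseline. The treatment estimate is the same as with baseline by time as a covariate. In those sets it carries no bias beyond that of the ANCOVA already chosen at 3 months.

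Three qualifications stand:

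- Twelve months is no longer the primary analysis time.
- The gain from age and sex is small, and the text ties them explicitly to the 3-month analysis, so their absence is a stated choice that fits poorly with the stated reason.
- The SEs are likelihood-based. The SAP does not say whether its multiple imputation precedes the 12-month model, and any effect of imputation is not included.

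**Conclusion.** The concern holds. The loss is one of precision; there is no bias and no change of estimand, and baseline still informs the 12-month means of dropouts through the unstructured covariance. The direction is firm for any ρ between 0 and 1 with equal variances. The absolute SEs and powers are illustrative because ρ, the 12-month dropout and equal SDs are assumed. For the change contrast the loss is noticeable at ρ = 0.5 and negligible at 0.8 and above; for the 12-month difference it is large and grows with ρ. The unnamed contrast is a defect at every ρ, because it leaves two different estimates consistent with the text. The 12-month section should be changed, but the primary 3-month conclusion does not depend on it.

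**What to change.** Keep the unstructured covariance and revise the mean model in one of two equivalent ways:

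- constrain the baseline means to be equal across arms, so that group enters only through the 3- and 12-month terms; or
- take 3 and 12 months as the responses, with baseline by time as a covariate.

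Add age by time and sex by time, for consistency with the 3-month analysis. State that the group contrast at 12 months from this model is the reported effect.

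As a minor wording point, change the exclusion of adjusted analyses under *Analysis population* so that it rules out only adjustment beyond the pre-specified baseline, age and sex.

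The cost is SAP wording and one changed model statement. No new data are needed.
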